1. INTRODUCTION

Influenza, commonly referred to as the flu, is an acute viral infection caused by RNA viruses of the family Orthomyxoviridae (the influenza viruses) (Eccles, 2005). Influenza viruses are known for high morbidity and mortality in humans and animals, and are a cause of acute respiratory diseases (WHO, 2009). Epidemics occur yearly during winter and, while most people recover from influenza, there are large numbers of people who need hospitalization and many who die from the disease. In United States, yearly on average, 5% to 20% of the population becomes infected with the influenza virus, more than 200,000 people are hospitalized from influenza-related complications, and approximately 36,000 people die from influenza-related causes (Centers for Disease Control and Prevention, 2009). Influenza causes serious public health and economic problems as a result of absence in the work force and productivity losses.

There are three types of seasonal influenza – types A, B and C. These types are further classified according to different kinds and combinations of virus surface proteins. Influenza is characterized by a sudden onset of high fever, chills, cough, headache, muscle and joint pain, weakness, general discomfort, sore throat and runny nose (Brankston *et al.*, 2007) and is often confused with the common cold, but is more severe and is caused by a different type of virus (Eccles, 2005).

The most effective way to prevent influenza or severe health outcomes from illness is by vaccination. The drawback to the vaccine is that it is most effective when circulating viruses are well-matched with vaccine viruses (Horwood and Macfarlane 2002). Antivirals such as Zanamivir and Oseltamivir (commonly known as Tamiflu) have been shown to inhibit both influenza A and influenza B virus replication *in vitro* (Blick *et al.*, 1998; Sidwell *et al.*, 1998; Li *et al.*, 1998). Further, Amantadine and Rimantadine have been used in the prevention and treatment of influenza viruses (Lu *et al.*, 2002). Annual epidemics are caused by antigenic shifts in influenza viruses, which results in modification of the virus, resulting in new virus subtypes (Kilbourne, 1975). Because antigenic shifts occur unpredictably, the general population has no immunity to the new subtypes and effective vaccines cannot be prepared in advance. As influenza viruses are constantly changing, the success of the vaccines is often in question. Further limitations are related to adverse effects of vaccines in some recipients, as well as the fear of vaccine causing the flu or other severe adverse health effects. As a result, approximately 15-20% of the population refrains from vaccination. An effective alternative treatment, medicine, or combination therapy for the treatment of influenza without side effects is therefore desirable.

Previous scientific studies on humic acid have shown that it exhibits anti-inflammatory (Kuhnert *et al.*, 1982) and antiviral properties (Mentel *et al.*, 1983). Humic acid is a high molecular-weight discotic molecule that is isolated from soil. Humates act as nutrients and media additives for soil microflora, and for the production of antibiotics in the soil (Huck *et al.*, 1991). Humic substances have been shown to exhibit antiviral properties against rhinovirus (Sydow *et al.*, 1986); recent studies have shown that humic acid impairs the attachment of human immunodeficiency virus (HIV) (Laub, 2000; Laub, 1995), herpes simplex virus types 1 and 2 (Helbig, *et al.*, 1987; Kloecking, 1991), influenza types A and B, and other respiratory tract infections (Laub, 2000; Sydow *et al.*, 1986). Previous studies have also suggested the broad antibacterial potential of natural and synthetic humic acids with varying degrees of sensitivity to test organisms. In one study the sensitivity ranged from 2500-1250 microorganisms/mL with natural humic acid, and 39 microorganism/mL with synthetic hydroquinone humic acid (Ansorg and Rochus, 1978). Recent studies have additionally shown the positive effects of humus

A Pilot Study to Investigate the Effects of Humic Acid on Flu Symptoms

Protocol 10HFHL

extract in Ayu fish against *Flavobacterium psychrophilum* infection (cold water disease) (Nakagawa *et al.*, 2009).

The mechanism of action of humic acid responsible for the inhibition of viral infection is believed to be the prevention of attachment of virus particles onto host cells (viral fusion inhibition), which in turn limits viral replication (Laub, 1999). *In vitro* studies of humic-like substances, for example, the oxidative polymer of protocatechuic acid (OP-PCA), have demonstrated the inhibition of replication of influenza virus A/WSN/33 (H1N1) in Madin-Darby canine kidney (MDCK) cells at concentrations of no cytotoxicity. It has also been demonstrated that humic acid inhibits the endonuclease activity of viral RNA polymerase (Lu *et al.*, 2001). (Influenza viral RNA polymerase plays an important role in viral RNA synthesis, which occurs after a virus has penetrated a host cell.) While humic acid is effective and may be added at any time after viral attachment, higher inhibitory effects are generally found when added at or prior to the stage of virus-cell fusion.

While previous *in vitro* and live-animal studies have demonstrated the therapeutic potential of humic acid, live-animal acute toxicity studies sponsored by Laub BioChemicals Corporation have additionally shown the material to be complete safety at levels of up to 50 mg/kg body weight. Thus, concentrations in the range of 50-2000 parts per million (ppm) are efficacious, yet not cytotoxic (Schiller *et al.*, 1979).

This study will be the first test of the effects of humic acid on flu symptoms in humans; the results will provide valuable information on influenza prevention and treatment.

2. STUDY OBJECTIVES

The primary objective of this study is to assess the efficacy of humic acid on flu symptoms as assessed by the alleviation of symptoms after 7 and 14 days of treatment in adults with influenza A or B. This will be determined by the use of a daily diary to assess the following symptoms during the trial on a 4-point scale (0=absent, 1=mild, 2=moderate, 3=severe):

[figure not shown]
- cough
- fever
- runny nose
- stuffy nose
- aches and pains
- headache
- chills
- sneezing
- ear aches
- fatigue

Additional endpoints will include:

- Visual analog scale (VAS) 0-100 mm, for ability to perform usual activities
- Doses of concomitant therapies for symptom treatment
- Immunological markers (WBC differential, CD4+, CD8+, TNF α , IL-8)

A Pilot Study to Investigate the Effects of Humic Acid on Flu Symptoms
Protocol 10HFHL

3. STUDY DESIGN

This is a multi-center, randomized, double-blind, placebo-controlled, parallel-group efficacy pilot study.

The study will consist of a single 14-day treatment period. Screening and randomization will occur on the same day.

The planned sample size for the study is 40 subjects, with 20 subjects randomized equally to each of the two study arms. The subjects will be recruited over the flu season.

Subjects will be randomized to one of the two treatment groups: Humic Acid or Placebo.

In order to evaluate primary and secondary endpoints, study assessments will be conducted at baseline, Day 7 and Day 14.

The study will be conducted at two sites in the US.

4. SELECTION OF STUDY POPULATION

The target population for this study consists of 40 adults with influenza A or B.

The study will be conducted in both male and female subjects of any ethnicity. Each subject will have to fulfill the inclusion criteria listed in Section 4.1. Subjects will not be included in the study if they meet any of the exclusion criteria listed in Section 4.2.

4.1 Inclusion Criteria

1. Male or female age 18 years or older
2. If female, subject is not of child bearing potential. Defined as females who have had a hysterectomy or oophorectomy, bilateral tubal ligation or are post-menopausal (natural or surgically with > 1 year since last menstruation)

–OR:

A Pilot Study to Investigate the Effects of Humic Acid on Flu Symptoms

Protocol 10HFHL

Female subjects of childbearing potential must agree to use a medically approved method of birth control and have a negative urine pregnancy test result. Acceptable methods of birth control include:

- double-barrier method (condoms with spermicide or diaphragm with spermicide)
 - hormonal contraceptives including oral contraceptives, hormone birth control patch (Ortho Evra), vaginal contraceptive ring (NuvaRing), injectable contraceptives (Depo-Provera, Lunelle), or hormone implant (Norplant System)
 - intrauterine devices
 - vasectomy of partner
 - abstinence
3. Positive diagnostic testing for influenza A or B by using rapid influenza antigen test (nasopharyngeal swabs)
 4. Illness as defined by onset or presence of respiratory symptom (cough, sore throat, nasal symptoms, sneezing) and one the following symptoms beginning within 48 hours before study enrollment:
 - fever ≥ 38.0 °C (≥ 100.4 °F) taken orally or subject report of fever within 24 hours prior to screening.
 - constitutional symptom [headache, myalgia (muscle pain), sweats/chills, fatigue]
 5. Available for all the visits scheduled in the study
 6. Receipt of any vaccine against influenza (based on verbal confirmation by the subject) for current season will be allowed
 7. Agreement to comply with study procedures and test article consumption
 8. Has given voluntary, written, informed consent to participate in the study

4.2 Exclusion Criteria

1. Women who are pregnant, breastfeeding, or planning to become pregnant during the course of the trial
2. Experienced any acute disease or infection requiring systemic antibiotic or antiviral therapy within the past 7 days
3. Cancer chemotherapy/radiation treatment within the 3 months prior to enrollment
4. Receipt of blood or blood products and/or plasma derivatives or any immunoglobulin preparation within 4 months prior to enrollment
5. Clinically significant acute respiratory distress
6. Chronic obstructive pulmonary disease (COPD)
7. Severe asthma (at the discretion of the Principal Investigator)
8. Known or suspected impairment/alteration of the immune system or immunocompromised (in the past 5 years)
9. Disorders of coagulation
10. Surgery planned during the study period
11. History of drug or alcohol abuse
12. Participation in a clinical research trial within 30 days prior to randomization
13. Allergy or sensitivity to study supplement ingredients
14. Individuals who are cognitively impaired and/or who are unable to give informed consent

A Pilot Study to Investigate the Effects of Humic Acid on Flu Symptoms

Protocol 10HFHL

15. Any other condition which in the Investigator's opinion may adversely affect the subject's ability to complete the study or its measures or which may pose significant risk to the subject

4.3 Concomitant Medications

The use of antibiotic or antiviral therapies within seven days of randomization is prohibited. Subjects who have received immunosuppressive therapies in the past 5 years or chemotherapy / radiation treatment within the 3 months prior to screening will not be enrolled into this study. Birth control is allowed during the study. Subjects who are currently taking prescribed birth control must agree to maintain their current method and dosing regimen during the course of the study.

Subjects will be allowed to use concomitant therapies for the treatment of symptoms (i.e., antipyretics, decongestants, expectorants, throat lozenges). Subjects will be asked to refrain from taking acetaminophen, aspirin, ibuprofen or NSAID within 4 hours prior to temperature readings.

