4.4 Early Withdrawal

Subject discontinuation should be considered at the discretion of the Principal Investigator. The circumstances of any discontinuation must be documented in detail. If possible, the evaluations planned for the end of the study will be carried out at the time when the subject is withdrawn from the study. A subject leaving the study prematurely will NOT be replaced by another. Criteria for removal of subjects from the study will include:

Personal Reasons. As stated in the Informed Consent Form, a subject may withdraw from the study for any reason at any time.

Clinical Judgment of Physician. A subject may be withdrawn from the study if, in the opinion of the Principal Investigator, it is not in the subject's best interest to continue. This includes but is not limited to adverse events or serious adverse events related to the investigational product causing clinically significant illness; the need for prohibited concomitant medication; female subject who becomes pregnant during the course of the trial.

Protocol Violation. Any subject found to have entered this study in violation of the protocol will be discontinued from the study at the discretion of the Principal Investigator. This will include any subject found to have been inappropriately enrolled (did not meet eligibility criteria). Subject non-compliance includes either not showing up for study visits, not taking investigational product as directed, or refusing to undergo study visit procedures. Subjects who are found to be taking prohibited medications or supplements without the knowledge of the Principal Investigator will also be withdrawn. Any major protocol deviations (i.e., those that increase the risk to subjects and/or compromise the integrity of the study or its results) will result in subject discontinuation.

A Pilot Study to Investigate the Effects of Humic Acid on Flu Symptoms

Protocol 10HFHL

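### The seven-day ban on antibiotics and antivirals has no direction, so sections 4.2, 4.3 and 4.4 do not settle its on-study status, and withdrawal under it can bias the symptom comparison either way

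*Protocol*

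**What the plan says.** Protocol section 4.3 (Concomitant Medications) states: "The use of antibiotic or antiviral therapies within seven days of randomization is prohibited". Antibiotics and antivirals are the only drug classes that this section calls prohibited. Its next sentence concerns enrolment and does give a direction: subjects with "chemotherapy / radiation treatment within the 3 months prior to screening will not be enrolled into this study". For the study period, section 4.3 permits a list of symptom treatments, which includes neither antibiotics nor antivirals.

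Exclusion 2 in section 4.2 deals with the same drug classes and looks back only: "Experienced any acute disease or infection requiring systemic antibiotic or antiviral therapy within the past 7 days".

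Section 4.4 (Early Withdrawal) acts on prohibited medication during the study in three ways. A subject may be withdrawn, at the Principal Investigator's judgment, for "the need for prohibited concomitant medication". For undisclosed use, withdrawal is mandatory: "Subjects who are found to be taking prohibited medications or supplements without the knowledge of the Principal Investigator will also be withdrawn". Major protocol deviations also lead to discontinuation. After a withdrawal, the end-of-study evaluations are done at that time if possible.

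The primary objective (section 2) is "alleviation of symptoms after 7 and 14 days of treatment in adults with influenza A or B", taken from a daily diary. Under section 8.2, missing symptom scores are not imputed, the average uses the days available, and the efficacy analysis takes subjects with at least one completed follow-up visit.

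**The concern.** A site needs to know whether an antiviral or antibiotic started during treatment is prohibited, and sections 4.2, 4.3 and 4.4 do not tell it. The event is foreseeable: every subject has tested positive for influenza A or B, and section 1 itself describes antivirals active against both types. With two sites, the sentence can be read in two ways within one trial of 40 subjects.

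The statistical stake lies in what follows. Starting such a drug is likely to be related to how ill the subject is, and so to the score being compared. If the event leads to withdrawal, section 8.2 makes the subject's score depend on when the diary stopped, or removes the subject altogether. Missing data of this kind can bias the comparison between arms, and the plan as written invites it.

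**Working it through.** The protocol gives no figure to reproduce here; section 8.1 says that no formal sample size calculation was made. The check has two parts.

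**1. The possible readings.** Set randomization at Day 0. Section 6.1 puts the first dose on the following day, so treatment runs over Days 1-14. Prohibited treatment days under each reading:

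- Before randomization only: 0 of 7 in Days 1-7 and 0 of 7 in Days 8-14.
- After randomization only: 7 of 7 in Days 1-7 and 0 of 7 in Days 8-14.
- Both sides: 7 of 7 in Days 1-7 and 0 of 7 in Days 8-14.

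On the first reading sections 4.2 and 4.3 agree, but the withdrawal rules of section 4.4 have no named on-study drug class to act on. On the other two, those rules apply to a start on Day 5 and not to a start on Day 10, and no passage states the status of these drugs on Days 8-14. No reading makes all three sections fit.

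**2. What withdrawal does to the comparison.** Inputs from the protocol: 20 subjects per arm (section 3), and ten symptoms scored 0-3 (Appendix 3), so 10 × 3 = 30 points if the items are summed. Everything else here is assumed: 3 placebo and 1 humic acid subject are withdrawn, and lower scores under humic acid mean benefit.

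*Case A: the subject leaves the efficacy set, having completed no follow-up visit.* Suppose those withdrawn score 6 points above their arm mean. Removing k of 20 lowers the arm mean by 6k/(20 − k).

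- Placebo, k = 3: 18/17 = 1.06.
- Humic acid, k = 1: 6/19 = 0.32.
- The difference shrinks by 1.06 − 0.32 = 0.74 points. With 2 against 1 it shrinks by 12/18 − 6/19 = 0.67 − 0.32 = 0.35.

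*Case B: the subject stays in the set with a shortened diary.* Suppose every score falls linearly from 20 on Day 1 to 0 on Day 14, so the score on day d is 20(14 − d)/13. The mean over a run of days is this formula at the middle of the run.

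- Days 1-4: 20 × 11.5/13 = 17.7.
- Days 1-7: 20 × 10/13 = 15.4.
- Days 1-14: 20 × 6.5/13 = 10.0.

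A diary that stops after Day 4 raises that subject's Day 1-14 average by 17.7 − 10.0 = 7.7 points. The placebo mean rises by 3 × 7.7/20 = 1.15 and the humic acid mean by 7.7/20 = 0.38, so the difference grows by 0.77 in favour of humic acid. On the Day 1-7 average the subject's rise is 17.7 − 15.4 = 2.3, and the difference grows by (3 − 1) × 2.3/20 = 0.23.

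Case B after Day 4 requires the withdrawal evaluation to count as a follow-up visit, which the protocol does not say. A stop after Day 5, inside the Visit 2 window of Day 7 ± 2, avoids that question: 20 × 11/13 = 16.9, and the Day 1-14 difference grows by (3 − 1) × 6.9/20 = 0.69.

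In both cases an equal split between arms gives no shift, and a reversed split reverses the sign.

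**The case against.** The best defence is that the text favours the backward reading. Exclusion 2 names the same drug classes and the same seven days, and the next sentence of section 4.3 is also an enrolment limit. Read so, the two halves of the treatment period are treated alike. This is plausible, but it leaves section 4.4 enforcing an on-study prohibition that no passage lists, so the sections still need to be reconciled.

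The defence does dispose of several stronger readings that a reader might infer:

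- *The same event is certainly handled in opposite ways in Days 1-7 and Days 8-14.* This follows under two of the three readings only. The boundary is also approximate, since Visit 2 has a window of ± 2 days, and section 2 does not define separate scores for the two weeks.
- *Use on Days 8-14 is allowed.* No passage says so. The permitted list covers symptom treatments, and silence is not permission.
- *On-study use always leads to withdrawal.* For a disclosed need withdrawal is discretionary; it is mandatory for undisclosed use or a major deviation. Discretion leaves more room for sites to differ.
- *The bias always runs towards no difference.* Case B above shows the opposite.

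It is also fair to say that concomitant therapy is already recorded in the diary and reviewed at each visit, and that a sensitivity analysis is commonly left to the SAP, so its absence is no fault here. But which drugs are prohibited, and on which days, is a rule that sites apply from the protocol, and the averaging rule is already fixed in section 8.2.

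**Conclusion.** The point holds as an inconsistency with a consequence for the primary comparison. Section 4.3 gives the window no direction, and under none of the three readings do sections 4.2 (item 2), 4.3 and 4.4 fit together for the 14 treatment days. Where withdrawal follows, the stated analysis lets the time of leaving determine the score.

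The size cannot be known from the protocol. Under the assumed 3 against 1 split, the shift ranges from 0.74 points against humic acid (whole subjects lost) to 0.77 points in its favour (diaries cut after Day 4, Day 1-14 average). These figures rest on assumed event counts, severity and recovery course, and on a summed score that the protocol does not define. Case B also assumes that the Day 14 result averages Days 1-14; if it covered Days 8-14 only, a diary stopped in the first week would contribute nothing to it. What the documents support is a possible bias of unknown direction. In a 40-subject pilot this is worth correcting but not fatal.

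**What to change.** Reconcile section 4.2 (item 2), section 4.3 and section 4.4 into one statement on antibiotics and antivirals that covers both the period before randomization and all 14 treatment days. Which rule applies is a clinical decision for the sponsor and investigators, and this review does not propose one.

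Whatever is decided, separate stopping study product from stopping data collection. Record the start date of any antiviral or antibiotic, continue the diary to Day 14 where the subject agrees, and analyse the subject as randomized over the same days as everyone else. Section 8.2 should then say that scores after such therapy are included at both time points. A sensitivity analysis that gives those days the subject's worst earlier score is optional and can be left to the SAP.

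The cost is a wording amendment and a few subjects keeping a diary that they would otherwise have stopped. Scores after such therapy will reflect it as well as the study product, so the comparison is of the arms as assigned.

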4.4 Early Withdrawal

Subject discontinuation should be considered at the discretion of the Principal Investigator. The circumstances of any discontinuation must be documented in detail. If possible, the evaluations planned for the end of the study will be carried out at the time when the subject is withdrawn from the study. A subject leaving the study prematurely will NOT be replaced by another. Criteria for removal of subjects from the study will include:

Personal Reasons. As stated in the Informed Consent Form, a subject may withdraw from the study for any reason at any time.

Clinical Judgment of Physician. A subject may be withdrawn from the study if, in the opinion of the Principal Investigator, it is not in the subject's best interest to continue. This includes but is not limited to adverse events or serious adverse events related to the investigational product causing clinically significant illness; the need for prohibited concomitant medication; female subject who becomes pregnant during the course of the trial.

Protocol Violation. Any subject found to have entered this study in violation of the protocol will be discontinued from the study at the discretion of the Principal Investigator. This will include any subject found to have been inappropriately enrolled (did not meet eligibility criteria). Subject non-compliance includes either not showing up for study visits, not taking investigational product as directed, or refusing to undergo study visit procedures. Subjects who are found to be taking prohibited medications or supplements without the knowledge of the Principal Investigator will also be withdrawn. Any major protocol deviations (i.e., those that increase the risk to subjects and/or compromise the integrity of the study or its results) will result in subject discontinuation.

A Pilot Study to Investigate the Effects of Humic Acid on Flu Symptoms

Protocol 10HFHL

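### Section 4.4 does not separate stopping product from leaving the study, so removal ends outcome collection for reasons that may be linked to prognosis

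*Protocol*

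**What the plan says.** Section 4.4 opens with a general sentence: "Subject discontinuation should be considered at the discretion of the Principal Investigator". It then introduces its list with "Criteria for removal of subjects from the study will include", so the level of withdrawal is the study and not only the product. The grounds differ in force:

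- **Mandatory.** Undisclosed use of prohibited treatment: "Subjects who are found to be taking prohibited medications or supplements without the knowledge of the Principal Investigator will also be withdrawn". Major deviations, which "will result in subject discontinuation".
- **Discretionary.** "the need for prohibited concomitant medication" is an example under the physician's clinical judgment, where the verb is permissive.
- **Implied.** Non-adherence is defined under the Protocol Violation heading, with no threshold and no verb of removal: "Subject non-compliance includes either not showing up for study visits, not taking investigational product as directed, or refusing to undergo study visit procedures".

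The only provision for data is this: "If possible, the evaluations planned for the end of the study will be carried out at the time when the subject is withdrawn". No diary entries or visits after withdrawal are described, and withdrawn subjects are not replaced.

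On what is prohibited, Section 4.3 says: "The use of antibiotic or antiviral therapies within seven days of randomization is prohibited". Exclusion 2 in Section 4.2 covers only the 7 days before entry. Section 4.4 also refers to prohibited supplements, but no section names one.

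Section 8.2 limits the efficacy analysis to subjects who complete one or more follow-up visits, imputes no symptom scores, and averages over the days that have data. Section 2 places the primary objective at 7 and 14 days.

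**The concern.** A subject can stop tablets and still give a full set of outcomes. Section 4.4 leaves no room for that: the grounds for leaving the study include matters of product use and concomitant treatment, and once a subject has left, the diary and remaining visits are no longer collected.

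The grounds are unlikely to be neutral. Antibiotics and antivirals are the only treatments Section 4.3 names as prohibited around randomization, and a subject whose influenza is getting worse is more likely to receive them. That links removal to prognosis. A link to treatment arm is an inference: efficacy or tolerability could change how often each arm meets these grounds.

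Section 8.2 makes the loss matter. Influenza symptoms usually fall over two weeks, so a diary that stops early keeps the worst days and loses the recovery. A subject who leaves before completing a follow-up visit drops out of the efficacy analysis. With 20 per arm and no replacement, a few such subjects can move the result.

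**Working it through.** **No figure to reproduce.** Section 8.1 states that no formal sample size calculation was done. The protocol gives no alpha, SD, effect size or dropout rate. The only arithmetic, 2 x 20 = 40, is consistent. What follows is illustration on assumed inputs.

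**Step 1: effect of a cut diary on one subject.** Assume a daily score proportional to exp(-(t-1)/tau) on day t, averaged over days 1 to k. The mean is [1 - exp(-k/tau)] / {k [1 - exp(-1/tau)]}. For tau = 5 days:

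- k = 5: (0.6321 / 0.1813) / 5 = 0.697
- k = 14: (0.9392 / 0.1813) / 14 = 0.370
- ratio: 0.697 / 0.370 = 1.88

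| Diary stops at | tau = 3 | tau = 5 | tau = 8 |
|---|---|---|---|
| Day 5 | 2.29 | 1.88 | 1.57 |
| Day 7 | 1.82 | 1.60 | 1.41 |

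Each entry is the available-day mean divided by the same subject's full 14-day mean. This takes the average in Section 8.2 to run over the whole treatment period.

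**Step 2: effect on the comparison when the product does nothing.** Score range: ten symptoms x 3 = 30 (Appendix 3), taking the sum as the score. Assumed: 20 per arm; starting score normal with mean 15 and SD 5, held within 3 to 30; tau log-normal with median 5 days and log-SD 0.4; slow recoverers preferentially removed; two-sided t-test at 0.05; 5,000 simulated trials. Of 20 subjects, 5%, 10%, 20% and 30% are 1, 2, 4 and 6. Removed subjects are either kept with 5 to 8 diary days, or excluded for want of a completed follow-up visit. Bias is humic acid minus placebo, so a negative value favours humic acid.

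| Removed, humic acid vs placebo | Kept: bias (type I error) | Excluded: bias (type I error) |
|---|---|---|
| 10% vs 10% | -0.01 (0.023) | -0.02 (0.051) |
| 5% vs 20% | -0.52 (0.039) | +0.30 (0.072) |
| 5% vs 30% | -0.87 (0.078) | +0.46 (0.083) |
| 20% vs 5% | +0.51 (0.042) | -0.28 (0.075) |

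With every subject followed to Day 14, type I error is 0.047 to 0.053, and no bias is expected because the arms are generated identically. The simulation error on a 5% rate is sqrt(0.05 x 0.95 / 5,000) = 0.003.

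The sign reverses between the columns. Keeping cut diaries makes the arm with more removals look worse; excluding the same slow recoverers makes it look better. Which column applies depends on when removal happens and on whether a withdrawal evaluation counts as a follow-up visit, which the protocol does not say. The type I error is a weaker guide than the bias: in the kept case it is below 5% at equal rates, and still below 5% with a bias of half a point.

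**Step 3: precision.** The difference detectable with 80% power at two-sided 0.05 is (1.960 + 0.842) x sqrt(2/n) SD. At n = 20 per arm it is 0.89 SD; at n = 16 it is 0.99 SD.

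**Step 4: can the rule be applied uniformly?** In Section 4.3, the seven-day window could lie before or after randomization. Exclusion 2 looks back, and the next sentence of Section 4.3 concerns enrolment, so the earlier period is a plausible reading. Section 4.4 nevertheless enforces a prohibition during the study and extends it to supplements. It also combines general discretion with mandatory wording. Two sites could read this differently and remove different subjects.

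**The case against.** The strongest reply is that the rule is softer than it looks and that its harm is easily exaggerated. Much of this stands.

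- A reader might infer that every subject who misses tablets or needs a prohibited medicine is removed. The text does not say so. Need for such medication is a permissive ground, non-adherence is only defined under the removal heading, discretion is stated first, and Section 5.5 lets a missed dose be taken later the same day.
- If the seven-day window in Section 4.3 looks back, on-study antivirals are not clearly prohibited, and the route from worsening illness to removal narrows. That stands as a limit on how often the rule would act.
- A reader might infer that the early evaluation would be analysed as Day 14. The protocol does not say that, and visit mapping is commonly left to the SAP, which is not shown.
- A reader might infer a large false-positive rate. Assuming removal at Days 3-5 of 15% vs 0% or 25% vs 5%, with all those diaries kept, one can reach a bias of 0.7 to 0.9 points and type I error of 14% to 22%. But Section 8.2 requires a completed follow-up visit, and Visit 2 falls at Day 7 ± 2, that is Days 5 to 9. Subjects removed on Day 3 or 4 would be excluded unless the withdrawal evaluation counts as a visit. Tablet counts are also made at visits, so non-adherence would usually come to light no earlier than Day 5.

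Allowed symptom relief, such as antipyretics, triggers nothing. What the reply does not answer is that two grounds are mandatory, that all grounds lead out of the study, and that no SAP can recover diaries that were never collected.

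**Conclusion.** The point holds as a design weakness that should be corrected. Stopping product and leaving the study are treated as one event, and after it the protocol provides for at most one evaluation on a variable day. This follows from the text and needs no simulation.

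Size and direction cannot be fixed from the document. Under the assumed recovery curves and preferential removal of slow recoverers, 5% against 30% removal gives about -0.9 points if cut diaries are kept and +0.5 if the subjects are excluded, with type I error about 8% in both cases. At 5% against 20% the shifts are -0.5 and +0.3. At equal rates of 10% the bias is about zero. The imbalance between arms is itself an assumption; the link to prognosis is plausible from the kind of medicines named, and the link to treatment is inferred.

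**What to change.** 1. In Section 4.4, separate stopping product from leaving the study. State that a subject who stops product, is non-adherent, takes a prohibited medicine or has a deviation continues the diary and the Day 7 and Day 14 visits unless consent to follow-up is withdrawn. Decisions on stopping product stay with the investigator.
2. Analyse all such data in the arm to which the subject was randomized.
3. Record any early evaluation with its actual study day, and say whether it counts as a completed follow-up visit for Section 8.2.
4. Reconcile Sections 4.2, 4.3 and 4.4 on whether the seven-day window lies before or after randomization, and on which medicines or supplements are prohibited during the study. This review takes no view on which they should be.

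The cost is protocol wording and contact with a few subjects at visits already scheduled. The small downside is that effect estimates will include time off product.
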